8.2. Sample Size and Power Considerations

The sample size of this study was calculated using a 2-sided α of 5%; power of 80%; RECIST response rate in the pembrolizumab arm is 30%; RECIST response rate in the pembrolizumab and radiotherapy arm is 50%. The study will randomise 234 patients in total (210 minimally required for statistical power calculation purposes, 105 patients in each arm; 20 additional patients to account for potential drop outs – an expected drop out rate of 10%) over 18 months i.e. 11-12 patients per month in approximately 15 to 24 UK centres. In the event that enrolment is slower than expected the Trial Steering Committee will consider adding additional UK sites. Patients enrolled in the trial are expected to be recruited from the routine clinics of the participating centres.

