8.3. Randomisation

Patients will be randomised in a 1:1 ratio to receive pembrolizumab alone or pembrolizumab in combination with radiotherapy using random permuted blocks within strata to take account of their LDH level at baseline and previous anti-CTLA4 treatment.

Randomisation of enrolled patients will be stratified based on the following parameters;

1. LDH (below or within normal range / above upper limit of the normal range) and
2. Previous anti-CTLA4 treatment (yes/no)

The randomisation number is a unique number. Patients will be identified using the number generated by the database which will become their unique identifier throughout the study and in all future correspondence..

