8.5. Planned method of analysis

Continuous data will be summarised using means, standard deviations, medians, minimum and maximum values and where appropriate 95% confidence intervals. Nominal and ordinal categorical data will be summarised using the number of observations and percentages. All significance tests will be two-sided using an overall alpha level of 5%. It is anticipated that adjustment will be made for repeated significance testing using a Bonferroni correction specifically for all secondary endpoints.

Primary Endpoint:

- The RR 12 weeks post treatment will be summarized as the percentage (including 95% confidence intervals) of responders and will be compared between treatment arms using the chi-squared test for proportions.

Secondary Endpoints:

- The RR at 6 months will be summarized as a percentage (including 95% confidence intervals) of responders and will be compared between treatment arms using the chi-squared test for proportions.

- To measure individual lesion response assessment every 12 weeks within each patient using McNemar's test of paired proportions between time points.
- The proportion of patients experiencing grade 3-5 toxicity will be compared on a regimen basis using the chi-squared test. Fishers exact test will be used when expected cell frequencies are <5.
- PFS and OS at 1, 2 and 3 years, respectively, will be calculated using Kaplan-Meier methods. Median PFS and OS with associated 95% confidence intervals will be presented by treatment and compared using the log rank test. Cox Proportional hazards regression model analysis will be used to calculate the hazard ratio between treatments along with its 95% confidence intervals and will be adjusted for other identified prognostic factors in a multivariate setting.

Exploratory Endpoints:

- Continuous exploratory data will be summarised using means, standard deviations, medians, minimum and maximum values attaching 95% confidence intervals where appropriate. Categorical data will be summarised using frequencies and proportions, attaching confidence intervals where necessary.

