8.6. Deviations from the Statistical Plan

Statistical methods to handle deviations from protocol (e.g. changes in final sample size) will be described in the analysis plan. The analysis plan of the handling and analysis methods of secondary variables may be updated following review of data during the study. The statistical analysis plan will be finalised / approved prior to the analysis. Deviations in implementation of the finalised analysis plan will be documented for affected results in the clinical study report.

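### Randomisation is stratified by LDH and prior anti-CTLA4, but the response and survival tests ignore the strata: mildly conservative if LDH is prognostic, and free to correct

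*Combined protocol and SAP*

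**What the plan says.** **Allocation.** Sections 4.3, 8.1 and 8.3 stratify the 1:1 randomisation by LDH (normal or below v above the upper limit) and prior anti-CTLA4 treatment (yes/no). Section 8.3 does so "using random permuted blocks within strata to take account of their LDH level at baseline and previous anti-CTLA4 treatment". That makes four strata.

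**Response.** Section 8.5 reports the 12-week response rate as the percentage "of responders and will be compared between treatment arms using the chi-squared test for proportions", and repeats this for 6 months. No stratified test or stratum-adjusted response model appears. Section 8.4.2 asks for the difference between arms, but attaches 95% confidence intervals only to the percentage in each arm.

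**PFS and OS.** These secondary endpoints are compared by a log-rank test with no strata. A Cox model gives the hazard ratio and "will be adjusted for other identified prognostic factors in a multivariate setting". The factors are not listed and are not tied to the two used at randomisation.

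**Later changes.** Section 8.6 says that the "handling and analysis methods of secondary variables may be updated following review of data during the study". It also requires the analysis plan to be finalised before the analysis and deviations to be documented.

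**The concern.** Balancing the arms within strata removes between-stratum differences as a source of chance variation in the treatment comparison. The plain chi-squared test still counts that variation in its standard error. If a stratum predicts response, the standard error is too large and the p-value too high. The test then rejects less than 5% of the time under the null, and some real effects are missed that the design had already paid to detect. The same holds for the log-rank test.

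What is at stake is efficiency and accurate calibration of the primary p-value. There is no added risk of a false positive.

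**Working it through.** **1. The plan's own figure (section 8.2).** Inputs: 30% v 50%, two-sided 5%, 80% power, 1:1.

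n per arm = [1.96·√(2·0.4·0.6) + 0.8416·√(0.3·0.7 + 0.5·0.5)]² / 0.2² = (1.358 + 0.571)² / 0.04 ≈ 93.

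With the continuity correction: (93/4)·[1 + √(1 + 4/(93·0.2))]² ≈ 103, close to the stated 105. Then 210/0.9 = 233.3, rounded up to 234. An uncorrected chi-squared test has 84.6% power at 105 per arm and 88.2% at 117 per arm, so there is a margin over 80%.

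**2. What the documents say about the strata.** They give no LDH prevalence, no LDH effect on response and no block size. For prior anti-CTLA4, the cohort in section 1.2.2 had almost equal response rates (38% with, 37% without), so that factor is taken as non-prognostic. The calculation therefore rests on an assumed LDH effect: 35% raised LDH, overall control rate 30%, odds ratio (OR) of response for raised v normal LDH from 1 down to 0.1.

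**3. Actual type I error of the plain test.** Let p_N and p_R be the null response rates with normal and raised LDH.

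- Variance assumed by the plain test, per patient: 0.30·0.70 = 0.21.
- Between-stratum part, removed by stratified allocation: B = 0.65·0.35·(p_N − p_R)².
- Ratio of true to assumed variance: r = 1 − B/0.21.
- Actual two-sided alpha: 2·[1 − Φ(1.96/√r)]. Sample size cancels.

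| LDH OR | p_N, p_R | B | r | 1.96/√r | Actual alpha |
|---|---|---|---|---|---|
| 1 | 0.300, 0.300 | 0 | 1 | 1.960 | 5.0% |
| 0.5 | 0.348, 0.211 | 0.0043 | 0.980 | 1.980 | 4.8% |
| 0.2 | 0.399, 0.117 | 0.0181 | 0.914 | 2.050 | 4.0% |
| 0.1 (extreme) | 0.425, 0.069 | 0.0288 | 0.863 | 2.110 | 3.5% |

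Simulation at N = 234 (100,000 trials per scenario) gave 4.8%, 4.2% and 3.5% for the last three rows.

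**4. Power gained by CMH (simulation, N = 234).**

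| LDH OR | Gain at 30% v 50% | Gain at 30% v 45% |
|---|---|---|
| 1 | none | none |
| 0.5 | about 0.1 points | about 0.5 points |
| 0.2 | about 1.5 points | about 3.5 points |
| 0.1 (extreme) | 2.7 points | 6 points |

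For scale, a separate run of 40,000 trials (blocks of 4 assumed) at N = 234 and 30% v 50% gave 88.9% to 89.1% at OR 0.5 and 89.6% to 90.8% at OR 0.25. At N = 210 the figures were 85.0% to 85.5% and 85.7% to 87.5%. With LDH not prognostic, CMH costs about 0.2 points (84.6% to 84.4% at N = 210), from slightly fewer effective degrees of freedom. The chi-squared test stays above 80% in every 30% v 50% scenario.

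**5. Log-rank (4,000 trials per scenario).** Assumed: 234 patients, 35% raised LDH, control median PFS of 7 months with normal LDH, treatment hazard ratio (HR) 0.68, censoring at 24 to 42 months.

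| LDH HR | Power, plain / stratified | Type I, plain / stratified |
|---|---|---|
| 1 | 80.7% / 80.3% | 5.6% / 5.7% |
| 1.5 | 79.2% / 80.8% | 5.1% / 5.4% |
| 2 | 78.5% / 82.5% | 3.8% / 4.8% |
| 3 | 70.5% / 80.4% | 3.1% / 5.1% |

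The Monte Carlo standard error of the type I figures is about 0.35 points, so the 5.6% is noise; the stratified test shows the same in those trials. The loss is about 4 points at LDH HR 2 and about 10 at HR 3.

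**The case against.** A plain chi-squared test matches the two-proportion sample-size calculation, is simple, and is valid in the sense that matters most: it does not raise the false-positive rate. The loss exists only if LDH predicts outcome, and the documents give no figure for that. At an LDH OR of 0.5 or weaker it is negligible, and the largest figures need an extreme effect. The 30% v 45% comparison is outside the design, and no power is planned for PFS or OS. All of this stands. It limits the point to an efficiency improvement.

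A reader might infer three stronger things that the documents do not support.

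- *That power is certainly lost.* It is lost only if a stratum is prognostic. On section 1.2.2, prior anti-CTLA4 contributes about nothing.
- *That the planned 95% confidence intervals are miscalibrated.* Sections 8.4.2 and 8.5 ask for intervals on each arm's percentage. These do not use the two-arm standard error, and no interval for the difference is specified. Only the p-value is affected.
- *That the Cox covariates will be picked from the data.* Section 8.5 leaves them unnamed but does not say they are selected after data review. Section 8.6 requires the plan to be final before the analysis, and its updating clause covers secondary variables only. Vagueness is a fair criticism; data-driven selection is not shown.

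**Conclusion.** The mismatch between allocation and analysis is certain from the text; its size is conditional. With 35% raised LDH assumed and N = 234, the primary test runs at about 4.8% at an LDH OR of 0.5, falling to 4.0% to 4.2% at 0.2 (3.5% at an extreme 0.1). CMH recovers about 0.1 to 1.5 points at the design effect and 0.5 to 3.5 points if the true rates are 30% v 45%. The loss may be larger for the secondary log-rank tests, about 4 points at an assumed LDH HR of 2.

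The primary comparison remains valid and adequately powered as planned. The change should be made because it is free, and the trial does not depend on it. LDH prevalence, LDH effect, block size and survival parameters are all assumptions. The response calculations use the chi-squared test without continuity correction, since section 8.5 does not say which is meant.

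**What to change.** In section 8.5 and the analysis plan:

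- **Primary endpoint:** compare 12-week response by a two-sided 5% CMH test stratified by LDH and prior anti-CTLA4, as recorded at randomisation. Report the stratum-adjusted risk difference with its 95% confidence interval, alongside the per-arm percentages already planned.
- **6-month response:** use the same method.
- **PFS and OS:** use a log-rank test stratified by the two factors, and a Cox model that names these two factors in place of the unlisted ones.
- **Sensitivity:** keep the plain chi-squared test, stating whether it is continuity-corrected.

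The cost is wording only. Both factors are already collected for randomisation, no new data are needed, and the sample size does not change. If LDH proves not to be prognostic, the price is about 0.2 points of power.

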8.5.1. Safety Review Meeting

To ensure the safety of the patients an assessment of toxicity of the first 6 randomised to receive both pembrolizumab and radiotherapy will be performed when they have completed 12 weeks of treatment. A listing of AEs will be produced for these patients identifying toxicity grades after they have completed 12 weeks of treatment.

8.6. Deviations from the Statistical Plan

Statistical methods to handle deviations from protocol (e.g. changes in final sample size) will be described in the analysis plan. The analysis plan of the handling and analysis methods of secondary variables may be updated following review of data during the study. The statistical analysis plan will be finalised / approved prior to the analysis. Deviations in implementation of the finalised analysis plan will be documented for affected results in the clinical study report.

8.7. Early Discontinuation of the Study

An interim analysis will be carried out when approximately 120 patients (50%) are evaluable for the primary endpoint, this will allow for the early termination of the trial should there be no difference between the two arms, respectively. No formal stopping rules are planned either for efficacy, futility or toxicity since this study is similar to routine standard of care with the addition of radiotherapy. The

Trial Steering Committee will monitor trial progress including for significant safety / toxicity issues should they arise.

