3.2.1 Additional Safety Evaluations

To ensure the safety of patients the 1st patient will be followed for 6 weeks or until the resolution of local acute toxicity to grade 1 before the second patient can begin treatment.

In addition the first 3 patients randomised to receive both pembrolizumab and radiotherapy will be seen weekly for the first 6 weeks of treatment to assess for any grade 3 or grade 4 toxicities. If no toxicity is seen the remaining patients in this arm will be seen as described above. If toxicity is seen an additional 3 patients from this arm should be seen weekly for the first 6 weeks.

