6.2.3. Radiotherapy techniques

Appropriate radiotherapy techniques should be used to ensure dose coverage of the irradiated lesions and to respect the organs at risk constraints as specified (see the current Radiotherapy QA Guidelines Manual for further information). It is envisaged that the majority of metastases to be irradiated will be those on the skin and in the superficial nodes, in which case either electron or 3D conformal radiotherapy can be used. The attending oncologist may choose to irradiate metastases in the liver, lung, para-vertebral region or deep seated nodes. In these cases complex IMRT or SBRT techniques may be appropriate and will be permitted.

As the radiotherapy fractionation schedule employed for this trial, 24Gy/3# is not a recognised palliative dose for melanoma at present, and giving it concurrently with Pembrolizumab is not the standard of care, maintaining the safety of patients recruited into the study should be our absolute priority. Therefore only CtE SABR centres with established clinical experience in irradiating sites close to critical organs at risk (such as mediastinal lymph nodes, thoracic oligometastases, hepatic metastases and paravertebral soft tissue metastases) in their routine clinical practice should irradiate these targets in this trial. Patient recruited at sites which are non-SARB CtE centres, patients will still receive pembrolizumab locally at the site but may be irradiated at other CtE centre.

It is anticipated that for centres with limited experience in delivering SABR, cutaneous metastases or superficial lymph nodes would be the most common targets for radiotherapy in this study.

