10.8.1.1. Safety Review Meetings

At the beginning of the study the TMG will meet every 2 weeks until the first 6 patients randomised to receive both pembrolizumab and radiotherapy have completed 12 weeks of treatment to review any safety aspects relating to the trial.

Once all 6 patients have completed 12 weeks of treatment a safety assessment will be conducted reviewing all AE's, SAE's and radiation toxicities occurring in this population.

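### The toxicity waiver in 8.7 rests on a reason that 6.2.3 undercuts, and early combination-arm toxicity has no stated, timed referral to the independent TSC members before the 50% review

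*Combined protocol and SAP*

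**What the plan says.** Section 8.7 states: "No formal stopping rules are planned either for efficacy, futility or toxicity". The same sentence gives the reason, waiving rules for "futility or toxicity since this study is similar to routine standard of care with the addition of radiotherapy". It then says that the "Trial Steering Committee will monitor trial progress including for significant safety / toxicity issues should they arise". Section 6.2.3 describes the added treatment differently: "24Gy/3# is not a recognised palliative dose for melanoma at present, and giving it concurrently with Pembrolizumab is not the standard of care".

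The protocol sets three early safety steps.

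- **First patient (3.2.1, 4.3).** The second patient cannot start until the first has been followed for 6 weeks or local acute toxicity has settled to grade 1. The hold is not limited to the combination arm.
- **First 3 combination patients (3.2.1).** They are seen weekly for 6 weeks to look for grade 3 or 4 toxicity. The stated consequence is: "If toxicity is seen an additional 3 patients from this arm should be seen weekly for the first 6 weeks".
- **First 6 combination patients (8.5.1, 10.8.1.1).** At the start, "the TMG will meet every 2 weeks until the first 6 patients randomised to receive both pembrolizumab and radiotherapy have completed 12 weeks of treatment". Then "a safety assessment will be conducted reviewing all AE's, SAE's and radiation toxicities occurring in this population". The statistical section adds: "A listing of AEs will be produced for these patients identifying toxicity grades after they have completed 12 weeks of treatment".

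Section 8.5 plans a chi-squared comparison of grade 3-5 toxicity between regimens. Section 8.4.1 sets a closed review by the independent TSC members at 50% recruitment. The only criterion written for that stage is RECIST response.

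**The concern.** Radiotherapy at this dose, given with pembrolizumab, is the randomised difference. The reason offered for having no toxicity rule therefore does not cover the component being tested.

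Followed as written, accrual to the combination arm continues whatever the first 3 or first 6 patients show, unless someone uses a general power to intervene. The first-6 assessment sits under the Trial Management Group (TMG) heading. The TMG's listed members (10.8.1) are the Chief Investigator, the Chief Co-Investigator, the statistician and the trial manager, and none is described as independent. Events will be reported quickly. What the protocol text does not supply is an agreed point at which independent members see them, with the control arm alongside, before half the trial is recruited.

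**Working it through.** The documents give no grade 3-5 rate and no toxicity threshold, so there is no plan figure to reproduce. The inputs from the plan are 1:1 allocation (8.3), 234 patients at 11-12 per month (8.2), and reviews at 50% recruited or about 120 evaluable (8.4.1, 8.7). Toxicity rates below are assumptions.

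**1. Toxicity levels and their consequences**

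| Step | Toxicity level stated | Trial-level action stated |
|---|---|---|
| First patient | Local acute toxicity to grade 1, or 6 weeks | Second patient waits |
| First 3 combination | Any grade 3-4 | None; weekly visits for 3 more |
| First 6 combination, week 12 | None | None; listing and assessment |
| 50% closed review | None (response only) | Continuance may be changed |
| Dose rules (6.3.8, 6.5, Appendix 4) | Graded | None; individual patient's pembrolizumab only |

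**2. Chance that the first-3 step is invoked.** P(at least 1 of 3) = 1 − (1 − p)³. At p = 10%, 20%, 30% and 40% this is 27%, 49%, 66% and 78%. It passes 50% only when p exceeds 1 − 0.5^(1/3) = 20.6%.

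**3. What six patients can show.** Even 0 events in 6 leaves a one-sided 95% upper limit of 1 − 0.05^(1/6) = 39%. A numerical bound at six patients would have little value; a referral does not depend on one.

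**4. Accrual during the first-6 window.** 12 weeks = 84/30.44 = 2.76 months. The combination arm gains 5.5 to 6 patients per month, so 5.5 × 2.76 = 15.2 to 6 × 2.76 = 16.6 patients enter while the sixth completes week 12. At half that pace it is 2.75 × 2.76 = 7.6.

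**5. When data reach the closed session, in radiotherapy-arm patients enrolled.** For n per arm at week 12, enrolment in the arm is (2n + 11 to 12 × 2.76)/2.

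| Look | Radiotherapy-arm patients enrolled, of 117 |
|---|---|
| 20 per arm at week 12 | 35-37 |
| 40 per arm at week 12 | 55-57 |
| 50% recruited (117 of 234) | 58 |
| 120 evaluable | 75-77 |
| 58 per arm at week 12 | 73-75 |
| 78 per arm at week 12 | 93-95 |

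Looks at 58 and 78 per arm would add little: the former nearly coincides with the 120-evaluable review and the latter falls after it. If the closed review is held at 50% recruitment, the 40-per-arm table can be part of it.

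**6. An example guide for the two earlier looks.** Flag for review when the posterior probability that the radiotherapy-arm grade 3-5 rate exceeds the control rate is above 0.95, with a Beta(0.5, 0.5) prior in each arm. With control at 20%, the flag needs 9 v 4 of 20 or 15 v 8 of 40. Exact two-arm binomial calculation gives the cumulative chance of a flag by the second look:

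| Assumed control rate | Equal arms | +10 points | +20 points |
|---|---|---|---|
| 15% | 8.3% | 35.7% | 71.8% |
| 20% | 8.2% | 33.0% | 68.0% |
| 30% | 8.4% | 29.3% | 60.9% |

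**The case against.** The strongest reply is that independent oversight of toxicity is already in place. The TSC has an independent chair, a duty under 8.7 to monitor toxicity, and a closed session that acts as IDMC without the co-chief investigators (10.8.2). SAEs are reported within 24 hours (7.5), SUSARs go to the regulator and REC (7.10), safety reports go to them annually (9.2.3), and urgent safety measures can be taken at any time (7.12). Section 6.2.3 raises the non-standard dose in order to impose a control: only experienced SABR centres may irradiate targets near critical organs. Lesion limits, credentialing and plan review add to this (6.2.2, 6.2.4). All of that stands. A reader might infer that no one independent watches toxicity; the documents do not support that.

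The clash between 8.7 and 6.2.3 is also only partial. Section 8.7 mentions the added radiotherapy and does not call the combination standard care. Its reason is weak for the tested component, but it is not a false statement about it.

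A reader might also infer that the first-3 step will probably be invoked, or that no toxicity criterion exists anywhere. The first needs a true grade 3-4 rate above about 21%, and the documents give none. The second cannot be said, because the TSC charter was not supplied.

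What survives is narrower. None of these provisions states that the first-3 or first-6 results go to the closed session, or that by-arm safety data reach it before the 50% review.

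**Conclusion.** The point holds as a specific gap that is cheap to close. The waiver's reason should not stand beside 6.2.3, and the two early steps should lead to independent members rather than only to more visits and a listing. Followed as written, some 15 to 17 further combination patients would be enrolled during the first-6 window, assuming steady accrual at the planned rate, and about 58 to 77 by the time of the 50% review, depending on which timing is used.

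The documents do not support a demand for a binding stopping boundary or a multi-look Bayesian rule. Such a rule would rest on assumed toxicity rates, and recording differs between arms: only the radiotherapy arm has radiation toxicity review and early weekly visits. A numerical guide is therefore the TSC's choice. Even the example guide, with control rates of 15-30%, detects a 10-point excess only 29-36% of the time by the second look. Confidence is medium, because the charter may already hold a criterion. The reason given in 8.7 would need correcting even then.

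**What to change.** 1. In 8.7, remove toxicity and the standard-of-care reason from the waiver. If the TSC charter holds a toxicity criterion, cite it there.
2. In 3.2.1, 8.5.1 and 10.8.1.1, send any grade 3-5 toxicity in the first 3 or next 3 combination patients, and the first-6 assessment whatever it shows, to the existing TSC closed session. State that the session decides whether to continue, pause or modify.
3. Give that session by-arm grade 3-5 tables, using the measure already in 8.5, at about 20 and 40 per arm at week 12 and at the existing 50% review. Leave any non-binding numerical guide for the TSC to set before the first table.

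**Cost.** A protocol amendment through the TMG, sponsor, REC, MHRA where required and site R&D (9.2.2, 10.7), best joined to the next one. About three to four closed sittings or circulations: the first-6 assessment, the two tables, and possibly an earlier one for the first 3. No new committee, visits or patients. If the example guide were adopted, about an 8% chance of an unneeded review with equal arms, possibly more because of the unequal recording.
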